After randomization, all patients (from both severe amblyopia and deprivation amblyopia groups) will have the following study visits/interactions:

Telephone Call

- Each patient will be contacted by the coordinator via telephone 4 weeks following the beginning of treatment to answer any questions and to encourage compliance with treatment.
- 12 ± 1 weeks after treatment begins : primary outcome visit

Primary Outcome Visit (occurs 12 ± 1 weeks after treatment begins)

Testing will include the following:

1. Visual acuity

Measured in each eye (worse eye first) by a certified examiner using the ATS single-surround HOTV acuity protocol.

2. Titmus fly and Randot Preschool Stereoacuity test

3. Ocular alignment assessed with the SPCT

4. Re-testing of visual acuity in the amblyopic eye (if indicated)

If amblyopic eye visual acuity has not improved from randomization by at least one line, then the acuity will be re-tested at this visit.

The results of the re-test will be used only to determine if the patient will continue study participation with the same study-mandated treatment. The first visual acuity will be used as the primary outcome visual acuity. If neither the test nor the re-test is one line better than the visual acuity at treatment, then study participation ends.

Efficacy of Intermittent Occlusion Therapy Glasses for Amblyopia-Dense, Deprivation and Myopic Anisometropia

Amblyopia

Approved 02/08/16

Amended: 05/12/16; 06/27/16; 06/29/16; 07/26/16, 09/13/16, 09/19/16, 09/27/16, 12/15/16, 01/26/17, 03/02/17, 06/20/17, 11/1/17, 12/19/17, 08/27/18, 12/18/18

Follow-Up Visits after the Primary Outcome Visit

For patients in either treatment group with at least one line of improvement in amblyopic eye acuity at the primary outcome examination, follow-up visits will occur every 12 ± 1 weeks until no improvement of one or more lines is seen.

At each post-primary outcome visit, visual acuity will be measured in each eye (worse eye first) by a certified examiner using the ATS single-surround HOTV acuity protocol. Acuity in the amblyopic eye will be re-tested during the visit if visual acuity has not improved from the last visit by at least one line.

Future treatment plans depend on each visual outcome in the amblyopic eye:

- If the patient's vision in the amblyopic eye is improved 1-2 lines, continue the study for another 12 weeks;
- If no improvement for one visit, continue the study for another 12 weeks;
- If no improvement for two visits, stop.

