Study participation will end only after a post-primary outcome visit at which amblyopic eye acuity shows no improvement of one or more lines on both an initial test and on a confirmatory re-test.

For all follow-up visits:

- Compliance will be evaluated with calendar log and microsensor.
- For patients who wear glasses with microsensors attached, data will be logged by connecting the microsensors to the reading station via antenna at 2-3 cm distance from the antenna. A USB cable transfers the data to a PC for storage; wearing times will be evaluated using the TheraMon® Software and compared to the wearing times protocol. Data will be recorded on the Follow-up Examination Form.

Test	Visit / Interaction			
	Enrollment	4 wk phone call	Primary Outcome 12 ± 1 wk (by masked examiner)	Every 12 ± 1 wks after primary outcome** (by masked examiner)
Telephone call		X		
Distance acuity each eye*	X		X	X
Ocular alignment	X		X	X
Titmus Fly	X		X	
Randot Preschool Test	X		X	
ATS questionnaire			X	X

* Using ATS single-surround HOTV acuity testing protocol on study certified vision tester.

** For patients whose amblyopic eye acuity has improved by ≥ 1 line at the 12-week visit, visits occur every 12 ± 1 weeks until no improvement of one or more lines.

Additional visits can be performed at the discretion of the investigator. A Follow-up Examination Form should be completed for every exam (not just the minimum required exams).

Extension Studies after Primary Outcome

Efficacy of Intermittent Occlusion Therapy Glasses for Amblyopia-Dense, Deprivation and Myopic Anisometropia

Amblyopia

Approved 02/08/16

Amended: 05/12/16; 06/27/16; 06/29/16; 07/26/16, 09/13/16, 09/19/16, 09/27/16, 12/15/16, 01/26/17, 03/02/17, 06/20/17, 11/1/17, 12/19/17, 08/27/18, 12/18/18

For patients who are randomized in the control patching group, after primary outcome at 12 weeks, if the patients desire to use IO-therapy glasses for treatment, they can use IO-therapy glasses for treatment as an extension study. This will not apply for those patients with deprivation amblyopia.

Stereoacuity

Differences between treatment groups in stereoacuity at the 12-week outcome will be assessed using a comparison of the distributions with the exact Wilcoxon rank sum test.

Primary Analysis for Safety

Sound Eye Acuity Data

The loss of 2 or more lines in sound eye visual acuity from baseline to the 12-week masked exam will be tabulated for each treatment group.

Ocular Alignment

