23. Financial Compensation for Participation.

The parent/guardian of each patient will be compensated \$25 for each follow-up visit, and \$50 for the primary outcome visit. For patients remaining in follow-up after the 12-week visit, \$25 will be paid for each 12-week interval visit, up to an additional \$100 (4 exams). All payments will be made using ClinCard. Subject would not be paid for a 5th or 6th visit.

Testing	Visit Schedule	Time	Payment
Enrollment testing		30-60 mins	\$25
Primary Outcome Visit	12 weeks after treatment begins	30-60 mins	\$50
Follow-Up Visits after the Primary Outcome*	12 weeks	30-60 mins	\$25
	12 weeks	30-60 mins	\$25
	12 weeks	30-60 mins	\$25
	Continue visits every 12 weeks until no improvement	30-60 mins	N/A
Total			

*follow-up visits will occur every 12 weeks until no improvement of one or more lines is seen.

* Definition of primary outcome: the 12-week exam visit is the primary outcome visit. For the patching group, after they switch to IO-therapy glasses, the first 12-week exam with IO-therapy glasses is also treated as the primary outcome visit.

SUBJECT IDENTIFICATION, RECRUITMENT, AND CONSENT (24-31)

24. Method of Subject Identification and Recruitment. Does the principal or secondary investigator have ethical/professional access to the names of potential subjects? If not, how will these names be obtained? How will prospective subjects be contacted for recruitment into the study? Attach a copy of any planned advertisements/notices. *Note: The identification and recruitment of subjects must be ethically and legally acceptable and free of coercion. In addition, the recruitment procedure should be designed to facilitate equitable selection of subjects with particular attention paid to the recruitment of study participants of both genders and from different racial/ethnic groups.*

Efficacy of Intermittent Occlusion Therapy Glasses for Amblyopia-Dense, Deprivation and Myopic Anisometropia

Amblyopia

Approved 02/08/16

Amended: 05/12/16; 06/27/16; 06/29/16; 07/26/16, 09/13/16, 09/19/16, 09/27/16, 12/15/16, 01/26/17, 03/02/17, 06/20/17, 11/1/17, 12/19/17, 08/27/18, 12/18/18

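### Does calling a patching child's first exam after the switch to IO-therapy glasses a primary outcome visit disturb the randomised comparison?

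*Combined protocol and SAP*

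**What the plan says.** Item 23 (Financial Compensation for Participation) carries a footnote to its payment table, worded as a definition of the primary outcome. It first says that "the 12-week exam visit is the primary outcome visit". For patching children who have switched, it then adds that "the first 12-week exam with IO-therapy glasses is also treated as the primary outcome visit". Nothing limits either statement to payment.

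The main text of item 23 pays 50 dollars for the primary outcome visit. For children followed beyond it, 25 dollars "will be paid for each 12-week interval visit, up to an additional" 100 dollars, which it equates with four exams. It adds: "Subject would not be paid for a 5th or 6th visit".

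Item 11 supplies the rest:

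- **Randomization of Eligible Patients** commits to intent to treat.
- **Extension Studies after Primary Outcome** lets patching children take up the glasses once the 12-week outcome is past, as an extension study. It gives no visit schedule for that phase.
- **Primary Outcome Visit** sets the re-test trigger ("If amblyopic eye visual acuity has not improved from randomization by at least one line") and says which reading counts: "The first visual acuity will be used as the primary outcome visual acuity".
- **Follow-Up Visits after the Primary Outcome Visit** uses a different trigger: acuity "will be re-tested during the visit if visual acuity has not improved from the last visit by at least one line".
- **The visit schedule table** marks the Titmus Fly and the "Randot Preschool Test" at enrolment and the primary outcome visit, but not at later visits.

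**The concern.** A sentence that reads as a definition of the primary outcome appears to create a second one for some children in one arm. If an analyst took it literally and counted post-switch exams as IO-therapy outcomes, the same child would contribute to both sides of the comparison. The second contribution would come from a child who chose the glasses after 12 weeks of patching. With 28 children per arm and an unknown number of switchers (assumed anywhere from 0 to 28), the IO side could hold 28 to 56 records against 28 for patching, or 56 to 84 records from 56 children. That would no longer be a randomised comparison.

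There is also a practical worry. The two visit types differ in payment, tests and re-test trigger, and no other sentence in the available text says which set applies to the post-switch exam. Several sites are recruiting, and they could handle it differently.

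**Working it through.** **1. Which exam feeds the group comparison?** Four statements bear on this.

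- Intent to treat keeps each child in the arm assigned (item 11, Randomization of Eligible Patients).
- The switch is available only after the 12-week outcome, so the 12-week value already exists before the child changes treatment.
- The later phase is called an extension study.
- The footnote says *also*. The first 12-week exam keeps its status and a later exam receives the same label.

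Ocular alignment is tied explicitly to 12 weeks after randomisation. Stereoacuity is compared between treatment groups at the 12-week outcome, and sound-eye loss is tabulated by group at the 12-week masked exam. Taken together, these place the comparison at the pre-switch exam. None of them says in so many words that the post-switch exam is excluded, so this is an inference, though a strong one. No analysis of extension exams appears in the available text.

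**2. Payment.** Inputs are from item 23: 25 dollars at enrolment, 50 at the primary outcome visit, and 25 per later exam up to four. The plan's own ceiling reproduces: 4 × 25 = 100 dollars after the first 12-week visit.

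| Treatment of the post-switch exam | After first 12-week visit | With enrolment and first outcome visit (25 + 50) |
|---|---|---|
| Paid 25, one of the four | 4 × 25 = 100 | 175 |
| Paid 50, one of the four | 50 + 3 × 25 = 125 | 200 |
| Paid 50, in addition to the four | 50 + 4 × 25 = 150 | 225 |

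The table, as extracted, shows three paid later exams rather than four. On that count the right-hand totals become:

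- 25 + 50 + 3 × 25 = 150
- 25 + 50 + 50 + 2 × 25 = 175
- 25 + 50 + 50 + 3 × 25 = 200

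The footnote speaks specifically about switched children, so it takes precedence over the general 25-dollar rule and points to 50 dollars. What it does not settle is whether the exam uses up one of the capped exams.

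**3. Assessments.** The primary outcome column has five: distance acuity, alignment, Titmus Fly, Randot Preschool and the ATS questionnaire. The later-visit column has three: distance acuity, alignment and the questionnaire. The difference is 5 − 3 = 2, the stereo tests. Taken at its word, the footnote selects the five-assessment set. The counts assume that the table columns were extracted correctly, but the Primary Outcome Visit text also lists the stereo tests.

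**4. Re-test reference.** As an illustration, assume a child gains 2 lines on patching and 0 lines over the first 12 weeks on the glasses. Change from randomisation is 2 + 0 = 2 lines, so no re-test is due. Change from the last visit is 0 lines, so a re-test is due. The two triggers can therefore disagree. Two facts limit the consequence:

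- The treatment-continuation bullet under Randomization in item 11 judges improvement across consecutive 12-week visits, which leans towards the last visit as reference.
- Under the primary-outcome rule, the re-test decides only whether participation continues, and the first reading is the outcome value. Under that rule the reference does not alter the acuity used as the outcome.

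**The case for a change.** The strongest case for a change is that this footnote is the only sentence in the available text on how the post-switch exam is treated, and a payment-only reading would settle nothing but the rate. The exam cap, the tests and the re-test reference would stay open. The primary outcome visit is also timed from the start of treatment, a phrase that for a switched child could mean either treatment. No sentence expressly bars the post-switch exam from the comparison, and a short clarification would cost almost nothing.

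Part of this stands. The exclusion is inferred, the cap is unclear (and the text and extracted table differ on four against three paid exams), and the re-test passages point to different references. Because the re-test bears on continuation, those passages must be reconciled with one another. No rule is proposed here.

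The rest carries less weight. Uneven stereoacuity or re-test data in the extension would matter if those data had a stated use, and the available text gives none. Whether families would be told different amounts depends on the consent form, which was not part of the text reviewed. Confining the footnote to payment could also work against the sponsor's intention, since it may have been meant to secure the full set of outcome tests after the switch.

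**Conclusion.** The concern does not call for a change to the plan. The footnote is loosely worded, but an analyst following intent to treat and the timing of the switch would use the pre-switch 12-week exam for both arms and report any post-switch exam separately. On that reading the effect on the randomised comparison is nil, and no sample size or power figure moves.

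The remaining uncertainty is administrative: 25 dollars on one exam and up to 50 dollars in total (150 − 100), two stereo tests, and a re-test reference that under the primary-outcome rule leaves the outcome acuity unchanged. These are matters for an editorial query at a convenient amendment.

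The conclusion rests on two assumptions. The first is that the pre-switch reading is the one applied. The second is that extension exams have no planned inferential use. The available text contains no paragraph naming the exam used for the primary acuity analysis, so it cannot confirm the first assumption directly.
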